2.4.2 Intervention description

The Baduanjin exercise group is asked to use the Baduanjin training system to practice the whole set of Baduanjin at least once a day and at least 5 days each week for 3 months. The Baduanjin training system is a video game designed with motion tracking and motion recognition strategy by the research team, providing a motivating full-body interactive experience for children with ADHD to engage in practice. Caregivers included in the Baduanjin intervention group were equipped with a Kinect sensor bar, connector, and software package on the day of enrolment. The software and electronic equipment installation is guided by researchers on the same day in the

hospital and at their homes later if necessary.

During the study, the children were asked to practice Baduanjin using the given software for at least 30 minutes daily, 5 times each week. They can practice any single brocade or the whole combination of 8 movements using the different game modes in the software. Instructions for movements and the variety of breath are provided in each game mode. The eight movements of Baduanjin are listed as follows:

1. Hold up the hands to regulate the triple burner;
2. Draw a bow like shooting a hawk;
3. Raise one arm to regulate the spleen and stomach;
4. Turn the head back to treat consumptive diseases and injuries;
5. Sway the head and swing the buttocks to expel the heart-fire;
6. Hold the feet by the hands to reinforce the loins and kidneys;
7. Punch with anger;
8. Hold and drop the heels to improve the health of the spine.

During their exercise, the child's motion will be captured and projected onto the screen, and their movement will be scored according to accuracy. The advice on motion adjustment is given immediately, and the feedback of data will be shown on the screen after each round of the game, then uploaded to a management website to be monitored by researchers.

The children in the Baduanjin group were asked to use the fitness tracker and uploaded data the same as the control group. The time of exercise is required to exceed 30 minutes each time, and the maximum heart rate during the exercise should be over 120 beats per minute. Researchers will also check with the data uploaded automatically by the Baduanjin software to ensure the movements are adequately practiced.

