2.5.1 Strategies to improve adherence to interventions

In this trial, each family has a Wechat discussion group where they can upload their biological data and contact the researcher conveniently. Researchers will check the uploaded data every

morning and give feedback to caregivers in the discussion group. When the data is not uploaded, researchers will remind the caregivers to upload data and make sure that if they have any difficulty in continuing the exercise. Researchers will also check the data uploaded automatically by the Baduanjin software to ensure the movements were adequately practiced. When unqualified exercise data is identified, the researcher will contact the caregiver to modify their exercise status and guide them to meet the requirement of exercise intensity and movement accuracy.

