2.5.2 Definition of adherence

Researchers will check the uploaded data every day. If the time of exercise exceeds 30 minutes, and the maximum heart rate during the exercise is over 120 beats per minute, it is recorded as a day that meets the adherence standard. For the participants in the Baduanjin group, the score automatically rated by the Baduanjin software should also exceed 77.5. We require the participants to meet the adherence standard for at least 5 days each week. Participants that finished less than 80% required days are defined as having poor adherence.

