#### *-Per-protocol population*

Participants will be excluded from the per-protocol population if their qualified exercise days (more than 30 minutes and the maximum heart rate during the exercise should be over 120 beats) less than 48 days. The experimental group in the per-protocol analysis will be defined according to what the participant actual receive. This population will be used for the supportive analyses.

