### **5.1.3. Covariate adjusted analysis of the primary outcome**

An analysis of the primary outcome will be adjusted for, sex (binary), admission height(continuous), admission weight (continuous), admission age (continuous), admission IQ score (continuous), regular exercise time prior to admission(continuous) and admission medical usage (using medicine or not when enrolled, binary) of the primary outcome by GLMM model (as described in 5.1.1).

If the above GLMM model does not converge, GLMM model will be performed with less covariates until coverage.

Covariate adjusted analysis will be performed on both mITT and PP populations.

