### **5.1.4. Subgroup analyses of the primary outcome**

Subgroup analyses will be performed for the primary outcome if each subgroup contains enough subject after stratification. We will stratify by sex (binary), categorized baseline medication usage (using medicine or not when enrolled, binary), qualified exercise days (less than 30/36/42/48 days, respectively, binary), categorized baseline exercise habit(binary), categorized baseline WFIRS score, and categorized baseline

SNAP score, respectively. (According to the scale rules, the continues variable will be transformed to the categorical variable.)

Subgroup analyses will be performed on both mITT and PP populations.

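### The SAP's per-protocol set forms the Baduanjin group by exercise received and counts days without the protocol's software-score rule, so it can hold children who did not follow their allocated exercise to the protocol's standard

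*SAP*

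**What the plan says.** SAP 4.2 excludes a child from the per-protocol population for having "qualified exercise days (more than 30 minutes and the maximum heart rate during the exercise should be over 120 beats) less than 48 days". The bracket is the SAP's whole definition of a qualified day, and the 77.5 score appears nowhere in the SAP. The next sentence reads: "The experimental group in the per-protocol analysis will be defined according to what the participant actual receive". The set is described as supportive.

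Protocol 2.5.2 sets the adherence standard. It uses the same time and heart-rate limits for both arms and adds: "For the participants in the Baduanjin group, the score automatically rated by the Baduanjin software should also exceed 77.5". It asks for at least five such days a week, and "Participants that finished less than 80% required days are defined as having poor adherence". Protocol 2.5.1 treats accuracy as something families must achieve, since researchers are to "guide them to meet the requirement of exercise intensity and movement accuracy". Protocol 2.4.2 says: "Researchers will also check with the data uploaded automatically by the Baduanjin software to ensure the movements are adequately practiced".

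The set is used in SAP 5.1.2 (per-protocol analysis), in SAP 5.1.3 ("Covariate adjusted analysis will be performed on both mITT and PP populations") and in the subgroup analyses of SAP 5.1.4. That last section also stratifies by "qualified exercise days (less than 30/36/42/48 days, respectively, binary"), in both the mITT and per-protocol populations.

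**The concern.** A reader will take a per-protocol result as the effect of the allocated exercise done to the protocol's standard. Two features of SAP 4.2 weaken that reading.

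- **Group by exercise received.** The comparison is no longer strictly between randomised arms. The SAP does not say how receipt is judged, how a child who did both kinds of exercise is placed, or whether a Baduanjin-randomised child who did another sport is excluded or becomes a control.
- **Day count without the score.** The score is the only part of the adherence standard that is specific to Baduanjin. Without it, half an hour of football above 120 beats per minute is a qualified day for a child randomised to Baduanjin, and so is a Baduanjin session with poor movements.

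The two gaps add up. The day count does not show which exercise was done, and the grouping sentence does not say how that is decided. Two analysts could build different sets from the same data.

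**Working it through.** **1. The 48-day cut.** The inputs are five days a week and the 80% limit (Protocol 2.5.2) and a three-month intervention (SAP 3.3). No number of weeks is given.

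- 12 weeks: 5 × 12 = 60 required days, and 0.80 × 60 = 48. This matches the SAP.
- 13 weeks: 5 × 13 = 65 required days, and 0.80 × 65 = 52. The cut of 48 would then be 48/65 = 73.8%.

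On a 12-week reading, the SAP's rule is the protocol's poor-adherence rule without the score condition. This link is an inference, because neither document states it.

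**2. How three Baduanjin-randomised children are classified**, each with 48 or more days that meet the time and heart-rate limits:

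| Child | Protocol 2.5.2 (12-week reading) | SAP 4.2 |
|---|---|---|
| Baduanjin, scores above 77.5 | adherent | in the set, Baduanjin |
| Baduanjin, scores never above 77.5 | poor adherence | in the set, Baduanjin |
| Other sport only | poor adherence (no qualifying score) | not excluded by the day rule; not Baduanjin; possibly a control |

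**3. Illustrative size.** The inputs from SAP 3.6 are a mean change of 3.52 for Baduanjin and 0.37 for routine exercise (both read as improvement) and an SD of 5.8. I take 60 per arm, half of the 120 randomised. The numbers of affected children and their mean changes are assumptions.

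- Reference difference: 3.52 − 0.37 = 3.15.
- Standard error (SE): 5.8 × √(2/60) = 1.059.

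*Low scorers kept in the set.* With k of the 60 Baduanjin children low-scoring and improving by m on average, the difference is ((60 − k) × 3.52 + k × m)/60 − 0.37.

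| k | m = 0.37 (like controls) | m = 1.945 (halfway) | m = 3.52 (like the others) |
|---|---|---|---|
| 3 | 2.993 (−0.157; 0.15 SE) | 3.071 (−0.079) | 3.15 (0) |
| 6 | 2.835 (−0.315; 0.30 SE) | 2.992 (−0.158) | 3.15 (0) |
| 12 | 2.520 (−0.630; 0.59 SE) | 2.835 (−0.315) | 3.15 (0) |

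*Switchers counted as controls.* Excluding them leaves 3.15. Counting k of them as controls gives 3.52 − (60 × 0.37 + k × m)/(60 + k).

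| k | m = −3 | m = 0.37 | m = 3.52 |
|---|---|---|---|
| 1 | 3.205 (+0.055) | 3.150 (0) | 3.098 (−0.052) |
| 3 | 3.310 (+0.160) | 3.150 (0) | 3.000 (−0.150) |

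For 3 switchers the shift is about 0.15 SE in either direction.

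**The case against.** **The protocol defines no per-protocol set.** This is correct. A reader might infer that the SAP contradicts a per-protocol rule in the protocol, but there is none: Protocol 2.5.2 defines adherence, and Protocol 2.15.1 names only the ITT population. The narrower point stands. A set labelled per-protocol implies the protocol's own standard, and 2.5.2 is the only passage that sets one by counting days.

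**Leaving out the score is defensible.** Time and heart rate apply equally to both arms. A score filter applies to one arm only and selects better performers after randomisation, with no counterpart among controls. This objection stands, and it is why the score rule should not simply be imposed. It supports showing both results.

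**The daily score is itself undefined.** Protocol 2.4.2 allows different game modes and gives feedback after each round. Protocol 2.5.2 does not say whether the best, mean or last round counts. This also stands, and any repair has to settle it.

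**Few children are likely to be affected.** The sensor and software are issued to the Baduanjin arm, so controls are unlikely to switch. Uploaded data are checked daily and families are contacted. Stopping exercise for two consecutive weeks without good reason counts as drop-out. All this makes large numbers less likely, but it does not say what happens to the children who remain.

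**The sizes are assumed.** No rate of low scores or of switching is given. The 3.52 comes from a pilot of 23 children with no stated score filter, so it may already include low scorers and the first table may overstate the loss. Keeping 60 per arm also ignores the 48-day filter and drop-out. The tables show scale only.

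**Conclusion.** The point holds for the supportive analyses. SAP 4.2 forms the experimental group by exercise received and leaves out the score that Protocol 2.5.2 requires for a Baduanjin day. The per-protocol set can therefore include children who did not do the allocated exercise, or did not do it to standard, and the text allows the former to be counted as controls. The number of such children is unknown. In the illustrations the shift runs from none to 0.63 points, and the largest value needs 12 of 60 children to score low and gain nothing over controls.

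Two stronger readings are not supported. One is that the primary result is compromised. It is not, because the mITT population depends on randomisation and an observed primary outcome, not on exercise days. The other is that the per-protocol analysis is wholly as-treated. It is a hybrid: the 48-day filter still applies, and the sentence speaks only of the experimental group, so at minimum it keeps a child who did another sport out of that group.

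The qualified-days subgroups in SAP 5.1.4 use the same term and probably inherit the same definition, including in the mITT population, but the SAP does not say so. The match of 48 days to 80% of required days assumes 12 weeks.

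**What to change.** In SAP 4.2:

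- State that per-protocol comparisons are by randomised arm, that only days of the allocated exercise count, and that children with fewer than 48 such days are excluded and not reassigned.
- Report any comparison by exercise received separately, labelled as-treated.
- Report the per-protocol result both with and without the 77.5 rule. Fix in advance how the daily score is taken, for example as the mean of that day's rounds. Give the number of Baduanjin children the rule removes, and note that it selects on performance in one arm only.
- State the number of weeks behind the 48-day cut.

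In SAP 5.1.4, say that the qualified-days subgroups use the same day definition.

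The cost is a few lines of wording and one or two derived variables. The tracker and software data are already uploaded under Protocol 2.4.2. However, the SAP's variable list shows no field identifiable as a software score, so the scores would have to be brought in from the management website. The supportive set may become slightly smaller. Randomisation, visits, sample size and the primary analysis do not change.

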#### *-Safety population*

Participants who were given any exercise-relate-treatment would be included in this population. Adverse reactions and events would be recorded. This population will be used for the supportive analyses.

### **4.3. Study Close Date**

The data collection close date is the date on which the last patient completed follow-up to achieve outcomes (complete 6 months follow-up).

### **4.4. Data Cleaning**

The data will then be checked to ensure that there are no erroneous entries and that all missing data is properly coded. Any changes will be made on the ACCESS database.

### **4.5. Data Check-up**

Once all data have been inputted and checked, the database will be locked and a data download request made. The data will be downloaded into SAS and R for statistical analyses.

## **5. Statistical Analyses**

### **5.1. Primary Outcome Analysis**

#### **5.1.1. ITT analysis of the primary outcome - the primary analysis**

The primary outcome is a repeated measured continuous variable, Hyperactivity/Impulsivity score change in doctor rated SNAP-IV scale. The primary analysis will be based on the mITT population as defined above. Generalized liner

mixed model (GLMM) will be performed using maximum likelihood (ML) method with treatment (binary) and time (ordinal) and interaction of treatment with time as fixed effect, and ID as random effect. Gaussian distribution and identity link function will be used in the GLMM model. Mean difference and 95% confidence intervals (CI) between groups at each time point will be estimated based on the fitted GLMM model.

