2.2.1 Inclusion Criteria

Inclusion criteria: (1) Age between 7 years 0 months to 16 years 11 months. (2) Diagnosed with ADHD at the clinic of the Child psychology department, with Combined Presentation or Predominantly Hyperactive-Impulsive Presentation. (3) Doctor version of SNAP-IV Hyperactivity/Impulsivity score ≥ 12 . (4) Full-Scale Intelligence Quotient ≥ 80 (Wechsler intelligence scale for children-IV). (5) Resident in Shanghai, Zhejiang province, and Jiangsu province. (6) The parents or caregivers can understand the content of the study, are willing to participate in the follow-up visits, and complete the required information.

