2.7 Participant timeline

Outcome measures are collected at enrolment, 3 months allocation, and 6 months post allocation. The flow of the trial is presented in Figure 1. A schematic diagram of enrolment, interventions, and assessments is described in Table 1.

TG: treatment group, CG: control group, SNAP-IV: The Swanson, Nolan, and Pelham Questionnaire

Figure 1 Flow diagram showing study design and subject allocation

Table 1 Enrolment, interventions, and assessments

| | STUDY PERIOD | | | |
|-------------|--------------|------------|-----------------|-----------|
| | Enrolment | Allocation | Post-allocation | Close-out |
| TIMEPOINT** | -2 Weeks | 0 | 3 months | 6 months |
| ENROLMENT: | | | | |

| | | | | |
|--|---|---|---|---|
| Eligibility screen | ✓ | | | |
| Informed consent | ✓ | | | |
| Allocation | | ✓ | | |
| INTERVENTIONS: | | | | |
| Baduanjin practice | ✓ | ✓ | ✓ | ✓ |
| routine physical exercise | ✓ | ✓ | ✓ | ✓ |
| ASSESSMENTS: | | | | |
| Primary Outcome: SNAP-IV clinician-rated Hyperactivity/Impulsivity score | ✓ | | ✓ | ✓ |
| Secondary Outcome: Scoring evaluation of the TCM symptoms(researcher rated) | ✓ | | ✓ | ✓ |
| Other outcome measures: | | | | |
| SNAP-IV parent/clinician-rated inattention and ODD score | ✓ | | ✓ | ✓ |
| WFIRS (parent completed) | ✓ | | ✓ | ✓ |
| CBCL (parent completed) | ✓ | | ✓ | ✓ |
| SDQ(parent and child completed) | ✓ | | ✓ | ✓ |
| CANTAB(child completed) | ✓ | | ✓ | ✓ |
| BRIEF-2 (parent completed) | ✓ | | ✓ | ✓ |
| DTVP-2(child completed) | ✓ | | ✓ | ✓ |
| Child Sensory Integration Checklist (parent completed) | ✓ | | ✓ | ✓ |

SNAP-IV: The Swanson, Nolan, and Pelham Questionnaire; TCM: Traditional Chinese Medicine; ODD: Oppositional Defiant Disorder; WFIRS: Weiss Functional Impairment Rating Scale; CBCL: Achenbach Child Behavior Checklist; SDQ: Strengths and Difficulties Questionnaire; CANTAB:

Cambridge neuropsychological test automated battery; BRIEF-2: Behavior Rating Inventory of Executive Function, Second Edition; DTVP-2: Visual Perception of children is measured by the Developmental Test of Visual Perception-2nd edition.

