### **3.6. Sample Size**

The sample size was calculated based on the primary outcome. According to our 3 months pilot study, the change score of Hyperactivity/Impulsivity assessed by doctor version of SNAP-IV scale in Baduanjin practice group (N=23) was 3.52 with a standard deviation of 5.81. Based on the outpatient data among ADHD patients, the mean change score Hyperactivity/Impulsivity assessed by doctor version of SNAP-IV scale in regular physical exercise patients was 0.37 with a standard deviation of 3.72. We assumed that the difference in the mean change score between Baduanjin practice group and regular

physical exercise group was 3.1 a standard deviation of 5.8. So as to demonstrate superiority with 80% of power and a significance level of 0.05 (two-sided), at least 56 participants for each arm will be required. With an anticipated a drop-out rate of 5%, a total of 120 participants need to be randomized.

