## 4. Analysis Consideration

### 4.1. Trial hypothesis

The hypothesis H0: “No difference in the change of Hyperactivity/Impulsivity score assessed by doctor version of SNAP-IV scale at 3th month between two groups.” will be tested against the alternative” H1: “The change of Hyperactivity/Impulsivity score assessed by doctor version of SNAP-IV scale at 3th month is different between two groups.”

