## **5.2. Secondary Outcome Analysis**

All secondary outcomes will be analyzed as for a superiority designed trial and two-sided significance with alpha=5% and standard 95% CIs for the treatment differences in these outcomes between two groups will be calculated and presented. Secondary outcome analyses will be based on the mITT population unless specified.

The continuous outcome such as weight will be summarized using number of subjects (n), mean, standard deviation (SD), minimum, and maximum by treatment group, and will be analyzed by a GLMM model. Mean differences with 95% confidence intervals between two groups will be derived from the GLMM model.

All the secondary outcomes would be analyzed in the same tactics of primary outcome described above.

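### The baseline clinician Hyperactivity/Impulsivity score is in neither the primary mixed model nor the covariate-adjusted model, and the levels of time are not listed

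*SAP*

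**What the plan says.** The primary model in SAP 5.1.1 is a Gaussian mixed model, fitted by maximum likelihood, for the change in the clinician-rated score, "with treatment (binary) and time (ordinal) and interaction of treatment with time as fixed effect, and ID as random effect". No other term is listed. The Protocol's version of the primary analysis (2.15.1) is a generalized linear model at 3 months and names no covariates.

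The adjusted analysis in SAP 5.1.3 lists "sex (binary), admission height(continuous), admission weight (continuous), admission age (continuous), admission IQ score (continuous), regular exercise time prior to admission(continuous" and, seventh, medication use at enrolment. If the model does not converge, covariates are dropped in no stated order. SAP 5.2 extends the approach: "All the secondary outcomes would be analyzed in the same tactics of primary outcome described above".

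The baseline score is available. Table 1 in Protocol 2.7 schedules "Primary Outcome: SNAP-IV clinician-rated Hyperactivity/Impulsivity score" at enrolment, and Protocol 2.2.1 makes it an entry criterion: "Doctor version of SNAP-IV Hyperactivity/Impulsivity score ≥ 12". Apart from forming the change score, its only planned uses are in baseline Table 1A and, in SAP 5.1.4, as a categorized subgroup factor.

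SAP 4.1 states the null hypothesis as "No difference in the change of Hyperactivity/Impulsivity score assessed by doctor version of SNAP-IV scale at 3th month between two groups". The levels of time are not listed in 5.1.1. SAP 2.2.1 gives the primary time frame as baseline and month 3, while shell Tables 2 and 3 show months 3 and 6 only.

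**The concern.** A change score does use baseline, but with a fixed coefficient of 1. It removes a chance baseline difference exactly only if the slope of follow-up on baseline is 1. With a slope below 1, the arm that happens to start higher will appear to improve more. An entry cut-off of 12 and imperfect reliability (Protocol 2.6.1 cites a test-retest ICC of 0.68) make such a slope plausible. Randomization is in blocks of 4 without stratification on severity, so the design does not limit a baseline difference either.

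At stake are the width of the primary confidence interval and how far the estimate depends on the draw of baseline scores. Table 1A would show an imbalance, but no planned whole-population analysis estimates the baseline slope and corrects for it. The analysis labelled covariate adjusted includes height and weight but omits the baseline of the outcome being analysed.

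A smaller matter is the levels of time. If baseline were entered as a visit, the model and its error rate would change.

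**Working it through.** **Inputs from the documents.** Difference 3.1, SD of change 5.8, two-sided 5% level, 80% power, 56 per arm (SAP 3.6: "physical exercise group was 3.1 a standard deviation of 5.8"). Scale range 0 to 27 (Protocol 2.6.1) with entry at 12 or more, so baseline lies between 12 and 27.

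**The plan's own figure.** The two-sample t-test needs 55.93, hence 56 per arm, and power at 56 per arm is 80.1%. Dropout: 56/0.95 = 58.9, so 59 per arm or 118 in total; the stated 120 is adequate. The half-width of the 95% CI is 1.982 × 5.8 × √(2/56) = 2.17 points.

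**Assumptions.** The documents give neither the baseline SD (s0) nor the baseline-to-3-month correlation (r). I take s0 from 3.5 to 5 and r from 0.3 to 0.5. For orientation, an even spread over the 16 scores 12 to 27 has SD √((16² − 1)/12) = 4.6.

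**Formulas.**
- Follow-up SD s1 solves 5.8² = s0² + s1² − 2·r·s0·s1.
- Slope of follow-up on baseline: b = r·s1/s0.
- Residual SD after adjustment: s1·√(1 − r²).
- Standard error of the baseline difference: s0·√(2/56).
- Shift in the unadjusted estimate from a one-SE imbalance: (1 − b)·s0·√(2/56).
- Power from the noncentral t, with 110 df unadjusted and 109 adjusted.

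**Worked case, s0 = 4, r = 0.4.** s1² − 3.2·s1 − 17.64 = 0 gives s1 = 6.09. Then b = 0.4 × 6.09/4 = 0.61, and the residual SD is 6.09 × √0.84 = 5.59. The variance falls by 1 − 5.586²/5.8² = 7.3%. The shift is 0.39 × 0.756 = 0.30 points.

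| s0, r | b | Residual SD | Variance cut | Power | CI half-width | n per arm for 80% | Shift, 1 SE | Shift, 1.96 SE |
|---|---|---|---|---|---|---|---|---|
| Unadjusted | – | 5.80 | – | 80.1% | 2.17 | 56 | – | – |
| 3.5, 0.5 | 0.96 | 5.80 | 0.1% | 80.1% | 2.17 | 56 | 0.03 | 0.06 |
| 4, 0.4 | 0.61 | 5.59 | 7.3% | 82.9% | 2.09 | 52 | 0.30 | 0.58 |
| 4.6, 0.3 | 0.34 | 4.93 | 27.6% | 90.9% | 1.85 | 41 | 0.58 | 1.13 |
| 5, 0.3 | 0.29 | 4.58 | 37.7% | 94.4% | 1.72 | 36 | 0.67 | 1.32 |

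Over a fine grid of these ranges, the medians are a 10% variance reduction, 84% power and a 0.35-point shift per one-SE imbalance. Adjusted power is nowhere below unadjusted power.

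**Levels of time.** Null trials were simulated with 2 × 56 children and a random-intercept ML fit: 20,000 trials per scenario, five (s0, r) pairs within the ranges above, and a 3-to-6-month correlation of 0.5 or 0.7. Type I error for the month-3 comparison was:
- Change at 3 and 6 months only: 5.0% to 5.6%.
- Change, with baseline entered as a level where every value is zero: 11.2% to 11.8%.
- Raw score with baseline as a level: 4.7% to 9.4% for the difference at month 3, and 4.2% to 8.1% for the treatment-by-time contrast.

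**The case against.** The best defence is that change score against baseline adjustment is a choice between two valid estimators. Subtraction is itself a form of adjustment, the estimate is unbiased over randomization, and the confidence interval already allows for chance imbalance. That is all correct, which is why this is not an error in the test or in the sample size. But subtraction imposes the slope, whereas adjustment estimates it at the cost of one degree of freedom.

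The second objection concerns size. The largest figures need s0 = 5, which is wider than an even spread over the permitted range. Capping s0 at 4.6 leaves a median variance reduction of about 8% and a maximum of 28%. Capping at 4.0 leaves about 5% and 16%. If r were 0.6 to 0.68 with s0 between 4 and 4.6, the gain would be 0 to 5%. These limits stand: the gain runs from nil to moderate.

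Third, SAP 3.6 reports SDs of 5.81 and 3.72 for the two arms. With those, unadjusted power is about 91.5%, so the need for extra precision is smaller. The gain does not disappear, and protection against imbalance is a separate matter.

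Fourth, the shells and the named response favour change at 3 and 6 months, where the error rate is sound, and SAP 4.1 already places the hypothesis at month 3. I agree, so the time levels are only a clarification.

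Finally, SAP 2.0 is dated October 2022, after the planned end of the study in March 2022. A late change to a primary model has a cost in credibility. This bears on how the fix is introduced, not on whether the gap exists.

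**Conclusion.** The concern holds and should be fixed. The baseline clinician score is missing from both models, and nothing elsewhere in the documents supplies it. The unadjusted analysis remains valid and 56 per arm stands.

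For s0 of 3.5 to 5 and r of 0.3 to 0.5, the half-width moves from 2.17 to between 1.72 and 2.17 points, and the sample needed for 80% power falls to between 36 and 56 per arm. The lower half of that benefit is the safer expectation, because the upper end needs a very wide baseline distribution. The gain vanishes when the slope is 1, and adjustment does not materially cost precision in any case examined. That the covariate is missing is certain; the size of the benefit cannot be fixed from the documents.

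**What to change.** - **SAP 5.1.1:** State that the response is change at 3 and 6 months and that time has those two levels. Add the baseline clinician Hyperactivity/Impulsivity score and its interaction with visit as fixed effects. Name the 3-month treatment contrast as the test of the hypothesis in 4.1.
- **SAP 5.1.3:** Add the baseline score, and say that it stays in the model if other covariates are dropped for non-convergence.
- **SAP 5.2:** Add the baseline value of the scale being analysed to each secondary model.
- **Optional:** REML with an unstructured covariance; its effect is minor.

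The cost is a few lines of text and code, with no new data and no more patients. The change should be dated and made before allocation is released to the study team. If allocation has already been released, keep the unadjusted model as primary and report the adjusted one as a clearly labelled sensitivity analysis.
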